The distribution of EFS will be estimated using the KM method. The KM curves and 25th, 50th (median), and 75th percentiles (if estimable), along with their 2-sided 95% CIs, will be presented for each treatment arm. The KM estimates at individual time points (eg, 3-, 6-, and 12-month rates) will be presented for each treatment arm. A Cox regression model stratified by randomization stratification factors will also be used to estimate the HR of EFS. However, given that the assumption of proportional hazards is not met based on the EFS definition, the overall HR is less meaningful in this context. As EFS is a composite endpoint, the estimates presented separately by each component are more meaningful: CR rate by 24 weeks and EFS among subjects who achieved CR by 24 weeks. For subjects who achieve CR by 24 weeks, the KM curves of the EFS distribution and 25th, 50th (median), and 75th percentiles (if estimable) along with their 2-sided 95% CIs will be presented for each treatment

arm. A Cox regression model stratified by randomization stratification factors will also be used to estimate the HR of EFS for these subjects.

It is assumed that the CR rate by 24 weeks is 20% and 40% for the placebo + azacitidine arm and the AG-120 + azacitidine arm, respectively. For subjects who achieved CR by 24 weeks, a target HR of 0.76 is assumed for EFS (equivalent to a median EFS among responders of 14.6 months in the placebo + azacitidine arm vs 19.2 months in the AG-120 + azacitidine arm, assuming an exponential distribution). Under these assumptions, a total of 173 EFS events are required to provide 80% power at a 1-sided alpha of 0.025 level of significance to reject the null hypothesis using a stratified log-rank test. Assuming a recruitment period of approximately 44 months, with an accrual rate of 3 subjects per month during the first 10 months and 5 subjects per month thereafter, along with an assumed 5% overall dropout rate, approximately 200 subjects will be randomized to the 2 treatment arms in a 1:1 ratio. Given the above assumptions, it is estimated that the analysis of the primary endpoint for EFS will occur approximately 52 months after the first subject was randomized.

Key Secondary Endpoint Analyses:

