8.5.2. Event-Free Survival Follow-up

All subjects who discontinue study treatment without experiencing any 1 of the following: death, disease relapse, treatment failure, or withdrawal of consent, will be followed every Day 1 (± 7 days) of Weeks 9, 17, 25, 33, 41, 53, and every 24 weeks thereafter for EFS until they experience treatment failure, relapse, death, withdraw from the study, or until the time when 173 EFS events have occurred or as deemed necessary by the IDMC.

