12.5.1. Analyses of the Primary Endpoint

The analysis for the primary endpoint will be performed at the time when 173 EFS events have occurred. Event-free survival is defined as the time from randomization until treatment failure, relapse from remission, or death from any cause, whichever occurs first. Treatment failure is defined as failure to achieve CR by Week 24. Subjects who do not achieve CR by Week 24 will be considered to have had an event at Day 1 of randomization. For the remaining CR responders, the event time will be the time of either disease relapse or death, whichever occurs first. Event-free survival will be censored upon initiation of a new anticancer therapy should a new therapy be initiated prior to any EFS event.

Event-free survival will be tested using the log-rank test stratified by the randomization stratification factors (de novo status and geographic region) based on the data in the ITT Analysis Set. The basis for a claim of efficacy will be the statistical significance of EFS in favor of the AG-120 + azacitidine arm when the 1-sided $p \leq 0.025$ (observed EFS HR ≤ 0.742).

The distribution of EFS will be estimated using the KM method. The KM curves and 25th, 50th (median), and 75th percentiles (if estimable), along with their 2-sided 95% CIs, will be presented for each treatment arm. The KM estimates at individual time points (eg, 3-, 6-, and 12-month rates) will also be presented for each treatment arm. A Cox regression model stratified by randomization stratification factors will also be used to estimate the HR of EFS. However, given that the assumption of proportional hazards is not met based on the EFS definition, the overall HR is less meaningful in this context. As EFS is a composite endpoint, the estimates presented separately by each component are more meaningful: CR rate by 24 weeks and EFS among those who have achieved CR by 24 weeks. For subjects who achieve CR by 24 weeks, the KM curves

of the EFS distribution and 25th, 50th (median), and 75th percentiles (if estimable) along with their 2-sided 95% CIs will be presented for each treatment arm. A Cox regression model stratified by randomization stratification factors will also be used to estimate the HR of EFS for these subjects. In addition, the ratio of restricted mean survival time, which does not rely on proportional hazards assumptions, between the 2 arms will also be presented to summarize the treatment effect.

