The treatment effects for the 2 components are clearly distinct and the assumption of proportional hazards will be violated. Therefore, instead of the overall HR, the assumptions for EFS are presented for the 2 components separately. Based on simulation results, the average overall HR over 10,000 simulations for the entire population is 0.641. However, the overall HR for the entire population was not part of the study design assumptions. Additionally, based on the current assumptions, for the overall population, the median EFS will be 1 day for both the placebo+azacitidine and AG-120+azacitidine arms.

Figure 2: Event-Free Survival under Protocol Assumptions

Abbreviations: EFS = event-free survival.

Under these assumptions, a total of 173 EFS events in approximately 200 randomized subjects with previously untreated IDH1m AML are required to provide 80% power at a 1-sided 2.5% level of significance to reject H_{01} using a stratified log-rank test (Table 3).

Table 3: Study Design Parameters for EFS

Design Parameters and Outcomes	
Power	80%
Significance level (1-sided)	2.5%
CR rate by 24 weeks (treatment vs control)	40% vs 20%
HR (treatment vs control) that can be detected for subjects who achieve CR by 24 weeks	0.76
Median EFS for subjects who achieve CR by 24 weeks (treatment vs control)	19.2 vs 14.6 months
Number of subjects randomized (1:1)	200
Target number of EFS events	173 EFS events
Accrual rate	3 subjects/month for the first 10 months, 5 subjects/month thereafter
Accrual time	44 months
Dropout rate	5%
Time to final analysis under H_{11}	52 months after first subject randomized

Abbreviations: CR = complete remission; EFS = event-free survival; HR = hazard ratio.

Overall Survival

Based on available data (Dombret et al, 2015), the median OS in the placebo+azacitidine arm is assumed to be 10.4 months. A target HR of 0.71 for OS (equivalent to a median OS of 10.4 months in the placebo+azacitidine arm vs 14.6 months in the AG-120+azacitidine arm, assuming an exponential distribution) is assumed. Based on 200 randomized subjects and the above assumptions, it is estimated that at the time of the final analysis for EFS, approximately 145 deaths will be observed. With 145 deaths, the study will have 54% power to detect a HR for OS of 0.71 at a 1-sided 2.5% level of significance using a stratified log-rank test.

CR, CR+CRh, and OR

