7.7.1.1.1. Determination of Event or Censoring for EFS

Evaluation of disease status, including evaluation of bone marrow and/or peripheral blood, is planned to be conducted at Screening (or as part of Pre-screening if within 28 days prior to randomization); Day 1 (± 7 days) of Weeks 9, 17, 25, 33, 41, 53, and every 24 weeks thereafter; at End of Treatment (EOT); during EFS follow-up on the same schedule; as clinically indicated; and/or any time that disease progression is suspected.

Determination of relapse date

Only disease assessments performed before the start date of subsequent anticancer therapies will be considered in the determination of relapse.

Confirmation is required for relapse. Assessments which are not done or not evaluable are ignored in the derivation of relapse confirmation. A subject will be considered to have relapsed if either of the following criteria are met:

- Relapse in 2 consecutive assessments that are at least 4 weeks apart
- Relapse with no further evaluable disease assessments before discontinuation from study or initiation of subsequent anticancer therapy

The date of relapse considered in the analyses will be the date when the first relapse, that is subsequently confirmed, is observed.

Determination of CR by 24 weeks

CR will be assessed until the date of relapse (that is subsequently confirmed). Only assessments performed on or before the start date of subsequent anticancer therapies will be considered in the determination of CR.

The protocol allows a 1-week window for disease assessments. Therefore, a subject will be considered to have achieved “CR by 24 weeks” if the date of first CR is within 25 weeks (24 weeks target+1 week window) after the date of randomization:

CR by 24 weeks if date of first CR–date of randomization $\leq 24 \times 7 + 7$.

Determination of two or more missing assessments

In the primary analysis of EFS, if a subject has an EFS event (relapse or death) after two or more missing disease assessments, the subject will be censored at the last adequate disease assessment documenting no relapse before the missing assessments. The followings are the rules for determining whether two or more disease assessments are missed.

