- If the event date is prior to day 1 of week 53 (relative day since randomization $\leq 52 \times 7 = 364$), and the difference of event date and the last adequate disease assessment $> (8 \times 2 + 1) \times 7 = 119$, then the event is considered as occurring after two or more missing disease assessments
- If the event date is between day 1 of week 53 and day 1 of week 77 (relative day since randomization > 364 and ≤ 532) and the difference of event date and the last adequate disease assessment $> (8 + 12 + 1) \times 7 = 147$, then the event is considered as occurring after two or more missing disease assessments
- If the event date is between day 1 of week 77 and day 1 of week 101 (relative day since randomization > 532 and ≤ 700) and the difference event date and the last adequate disease assessment is $> (12 + 24 + 1) \times 7 = 259$, then the event is considered as occurring after two or more missing disease assessments
- If the event date is after day 1 of week 101 (relative day since randomization > 700) and the difference of event date and the last adequate disease assessment is

$>(24+24+1)\times 7=343$, then the event is considered as occurring after two or more missing disease assessments

The outcome (event or censor), type of event and the date of event or censoring to be considered for the primary analysis of EFS are presented in Table 5.

Table 5: Outcome and Event or Censoring Dates for EFS

Scenario	Date of event/censoring	Event (event type)/ Censored
CR by 24 weeks ^a then relapse	Date of relapse	Event (relapse)
CR by 24 weeks ^a then death (no relapse)	Date of death	Event (death)
CR by 24 weeks ^a then start subsequent anticancer therapy (prior to relapse or no relapse)	Date of the last adequate disease assessment documenting no relapse prior to start of subsequent anticancer therapy or missed response assessments	Censored
CR by 24 weeks ^a then relapse or death after two or more missing or inadequate disease assessments		Censored
CR by 24 weeks ^a and neither relapse nor death		Censored
On treatment ≥ 24 weeks without CR by 24 weeks ^a	Date of randomization	Event (TF, on treatment ≥ 24 weeks without CR)
Treatment discontinuation prior to 24 weeks, without CR by 24 weeks ^a		Event (TF, treatment discontinuation prior to 24 weeks without CR)

Abbreviations: CR = complete response; EFS = event-free survival; TF = treatment failure.

^a Based on the protocol schedule of assessments, "+1 week window" is allowed.

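### The SAP's second relapse criterion omits data cutoff, so a single unconfirmed relapse in a responder who is on study and untreated at cutoff is censored at the previous relapse-free assessment

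*SAP*

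**What the plan says.** SAP 7.7.1.1.1 makes confirmation a condition of relapse and gives two routes. The first is relapse at two consecutive assessments at least 4 weeks apart. The second is "Relapse with no further evaluable disease assessments before discontinuation from study or initiation of subsequent anticancer therapy". A relapse that qualifies is dated at its first observation. SAP 6.4.1 excludes data after cutoff from analyses and imputations, so a confirming marrow after cutoff cannot be used.

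Table 5 censors responders who have neither relapsed nor died at the "Date of the last adequate disease assessment documenting no relapse prior to start of subsequent anticancer therapy or missed response assessments". Table 6 gives those still in the study a censoring reason that describes them as ongoing and free of relapse.

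On getting the second assessment, the protocol is not uniform:

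- The footnote to Table 10 asks for a repeat marrow at least a month later and warns that a transient blast rise can be a treatment effect.
- Section 8.5.2 admits to EFS follow-up only subjects who stopped treatment without relapse, and follows them "until they experience treatment failure, relapse, death, withdraw from the study".
- Section 10.7 and footnote 12 of Table 6 refer to sampling that continues on the schedule in use when the EFS event occurred.
- Scheduled assessments are 24 weeks apart after Week 53. Unscheduled ones are allowed.

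Sensitivity analysis 1 (SAP 7.7.1.2) uses actual relapse dates and lifts the missed-assessment and new-therapy rules. Neither it nor the other four analyses waives confirmation.

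**The concern.** Whether one relapse assessment counts as an event depends on what the subject does next, not on the assessment. Followed by study exit or new therapy, it is an event on its own date. Followed by cutoff, it becomes a censoring on an earlier date, chosen because relapse was seen afterwards. Censoring that depends on an observed sign of the event is informative. It touches the responder part of the primary endpoint, and so also the RMST comparison and the duration endpoints, which use confirmed relapse. A programmer who follows the text would apply it without noticing, because Table 6 has no separate category for these subjects.

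**Working it through.** **1. Trace one subject.** Take a responder who is relapse-free at Week 53, shows relapse at the Week 77 assessment, and reaches cutoff 2 weeks later, alive, on study and untreated.

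- Criterion 1: only one relapse assessment, so not met.
- Criterion 2: neither study exit nor new therapy, so not met.
- Table 5: the only row left is no relapse and no death. The subject is censored at Week 53, 24 weeks before the relapse on file.
- Had new therapy started the day before cutoff, criterion 2 would be met, with an event at Week 77.
- Had the subject died before cutoff, criterion 2 would also be met, because Protocol 8.5.4 lists death as a reason for study withdrawal.

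**2. Reproduce the plan's figures.** SAP 6.2.1 plans "a total of 173 EFS events in approximately 200 randomized subjects" for 80% power at 1-sided 2.5%, and the protocol gives the boundary as "observed EFS HR ≤ 0.742".

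- Boundary: exp(−2 × 1.96/√173) = 0.742, as stated.
- Power by simulation. Inputs: CR by 24 weeks 20% vs 40%; exponential responder EFS with medians 14.6 and 19.2 months; 3 subjects/month for 10 months, then 5/month to month 44; 5% dropout; failures are events at day 1. The log-rank test is unstratified, because strata proportions are not given. Result: 81.5% with cutoff fixed at month 52 (mean 177 events) and 80.7% with an event-driven cutoff (mean 176 events, month 50.4). The stated 80% is reproduced within 2 points.

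**3. Bound the number at risk.** Responders: 100 × 20% = 20 and 100 × 40% = 40. Hazards: ln2/14.6 = 0.0475 and ln2/19.2 = 0.0361 per month. Expected responder events in the last w months before cutoff C, summed over arms with n responders each:

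n × ∫ a(s) [F(C − s) − F(C − s − w)] ds

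Here a(s) is 3/200 per month up to month 10 and 5/200 from then to month 44, and F(t) = 1 − exp(−λt). Dropout is ignored. All subjects need 24 weeks of follow-up (SAP 2), so the earliest cutoff is 44 + 24 × 7/30.4375 = 49.5 months.

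| Cutoff (month) | All responder events | In last 4 weeks | In last 24 weeks |
|---|---|---|---|
| 49.5 | 35.9 | 0.89 | 5.9 |
| 52 | 38.1 | 0.80 | 5.3 |

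These window counts include deaths, and subjects whom criterion 2 already covers.

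**4. Estimate how many are censored.** The simulation was extended so that relapse is detected at the next scheduled visit, with cutoff at month 52. Assumptions not in the documents: 70% to 100% of responder events are relapses; 0% to 50% of relapsed subjects promptly start new therapy or leave; median survival after relapse is 6 months. Each setting had 1,500 replicates. The last two columns show the setting with the most affected subjects (100% relapses, 0% prompt exit).

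| When the confirming marrow is done | Affected, mean per trial | Mean events, literal rule vs counted | Power, literal rule vs counted |
|---|---|---|---|
| About 4.5 weeks after relapse | 0.3–0.9 | 174.2 vs 175.0 | 81.5% vs 81.5% |
| Next scheduled visit | 1.2–3.2 | 172.0 vs 175.2 | 82.9% vs 82.9% |
| Never | 3.0–8.4 | 166.6 vs 175.0 | 84.3% vs 83.3% |

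Power should be compared within a row only: the Monte Carlo standard error is about √(0.82 × 0.18/1500) = 1 point. Over all settings the within-row change was about 1 point or less.

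**5. By arm.** In the same settings 64% to 66% of affected subjects are on AG-120 (for example 2.13 of 3.23). That reflects its larger number of responders. Per responder the shares are close: 1.09/20 = 5.5% on placebo and 2.13/40 = 5.3% on AG-120 when confirmation waits for the next scheduled visit.

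**The case against.** The best defence is that one positive assessment is a suspected relapse. The protocol asks for a repeat marrow because blast rises can be transient. After study exit or new therapy, confirmation can no longer be obtained under the SAP, which is a reason to accept one assessment there. At cutoff it is only pending, and leaving pending cases uncounted is a defensible choice. The rule is also the same in both blinded arms, so it gives no evident reason for type I error inflation.

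Much of this stands. A reader might infer that the SAP discards real relapses; the documents support only documented but unconfirmed ones. A reader might also infer from Protocol 8.5.2 that a second marrow would never be done. The Table 10 footnote asks for one, and Section 10.7 points to continued sampling. What can be said is that confirmation depends on sites acting on the footnote, since 8.5.2 provides no EFS follow-up visit after relapse.

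The defence does not explain why the censoring date moves back to before the observed relapse, or why the subject is reported as free of relapse. Nor does the SAP say that pending cases were meant to be left out. Elsewhere it names the cutoff where it wants it to apply, for example for AE end dates, last dose and death date (SAP 6.5).

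**Conclusion.** The gap is in the text, and the resulting censoring of the primary endpoint is informative. It is minor in size: under 1 event with a prompt repeat marrow, about 1 to 3 if confirmation waits for the next scheduled visit, and about 3 to 8 only if no marrow follows relapse, which would go against the Table 10 footnote. These figures rest on the assumed relapse share, exit rate and post-relapse survival given with the simulation.

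Three stronger readings are not supported:

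- **About 6 events lost.** The 24-week window count of 5.3 to 5.9 includes deaths and subjects already covered by criterion 2. The matching simulated range is 1.2 to 3.2.
- **Lost power or a seriously delayed trigger.** Under the assumed CR rates, 80 + 60 = 140 events are Day 1 treatment failures, which the rule does not touch. SAP 2 sets the cutoff prospectively and accepts deviation from 173.
- **Bias towards one arm.** Affected subjects are proportional to responders, and no shift in the hazard ratio or p-value was calculated.

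The reason to act is a clear and consistent primary endpoint.

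**What to change.** Preferred: extend the second criterion in SAP 7.7.1.1.1 so that a single relapse counts when no further evaluable assessment exists before the earliest of study discontinuation, start of subsequent anticancer therapy, or data cutoff, with the event dated at that relapse. A later relapse-free assessment before cutoff would still overturn a transient rise.

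Alternative: keep the primary rule, add a sensitivity analysis that counts unconfirmed relapses at cutoff as events, and give these subjects their own censoring reason in Table 6.

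Either is a short SAP edit to make before unblinding. The preferred version has one cost: a few transient blast rises near cutoff could be counted as relapse. The protocol passages on sampling after relapse (Section 8.5.2, Section 10.7, footnote 12 of Table 6, and the Table 10 footnote) should also be reconciled.

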All subjects will have the extent of their disease assessed by bone marrow aspirate (extent of disease may be assessed by biopsy if standard of care or in the event of a dry tap or aspicular [diluted] sample) and peripheral blood samples at Screening (or as part of the Pre-screening process, as long as it is within 28 days prior to randomization); and Day 1 (\pm 7 days) of Weeks 9, 17, 25, 33, 41, 53 and every 24 weeks thereafter; at EOT; during EFS follow-up on the same schedule; as clinically indicated; and/or any time that disease progression is suspected. The disease assessment schedule should not be altered due to changes in the start of treatment cycles (eg, in the case of a treatment interruption that resulted in a delay to the start of subsequent cycles).

During treatment, response will be evaluated by the Investigator based on modified IWG Response Criteria for AML (Cheson et al, 2003) and European LeukemiaNet (ELN) guidelines (Döhner et al, 2017) to determine subject status and continuation on study treatment (see Section 10.8.1). Investigator response assessments will be used for the analysis of all efficacy endpoints, unless otherwise defined.

All subjects will undergo safety assessments throughout the treatment period, to include physical examination, vital signs, ECOG PS, ECG, ECHO or MUGA for LVEF as clinically indicated (method per institutional standard of care, with the same method used for an individual subject throughout the study; sites in Germany may only use ECHO), clinical laboratory assessments (hematology, chemistry, coagulation), and assessment of AEs, AESIs, SAEs, AEs leading to discontinuation or death, and concomitant medication use. Toxicity severity will be graded according to the National Cancer Institute Common Terminology Criteria for AEs (NCI CTCAE) version 4.03.

Safety data will be reviewed regularly by an IDMC to ensure the safety of the combination therapy. These reviews will occur after the first 6, 12, 24, and 36 subjects have completed 1 cycle of therapy or discontinued, whichever should occur first. Thereafter, safety reviews will be conducted approximately every 6 months until the study is unblinded for the analysis of the primary endpoint. No interim analyses for efficacy are planned.

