9.7. Study Drug Preparation and Administration

Subjects may not receive study treatment for each treatment cycle until all Day 1 procedures have been completed and all doses of study treatment from the prior treatment cycle have been accounted for, including the number of missed doses (where applicable). For females of reproductive potential, a serum β -hCG pregnancy test (sensitivity of at least 25 mIU/mL) must be performed at Screening within 72 hours prior to study treatment administration and be verified as negative.

The first day of study treatment dosing is considered Day 1 of a cycle.

Subjects will be monitored for hematologic toxicity and non-hematologic (if thought to be causally related) toxicity, with the NCI CTCAE version 4.03 used as a guide for the grading of severity (see Section 11.2). Dosing interruptions or delays or dose modifications may occur for managing toxicities and/or treatment response during study treatment (see Section 9.8).

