- 4 All subjects who discontinue study treatment without experiencing any 1 of the following: death, disease relapse, treatment failure, or withdrawal of consent, will be followed every Day 1 (± 7 days) of Weeks 9, 17, 25, 33, 41, 53, and every 24 weeks thereafter for EFS until they experience treatment failure, relapse, death, withdraw from the study, or until the time when 173 EFS events have occurred or as deemed necessary by the IDMC.
- 5 Screening bone marrow aspirate (or peripheral blood sample if bone marrow aspirate is not available, with Medical Monitor approval) will be collected for central confirmation of IDH1-mutated disease prior to randomization, and can be conducted before the 28-day Screening window.
- 6 A buccal swab for germ-line mutation analysis will be obtained at Screening.
[REDACTED]
- 8 Subjects should start study treatment (ie, C1D1 [Week 1]) within 3 days (72 hours) of randomization.
- 9 Prior to first dose of study treatment, only AEs that are classified as SAEs deemed related to study procedures should be reported. After initiation of study drug, all AEs and SAEs, regardless of attribution, will be collected. Subjects will be assessed at the Follow-up Visit (4 weeks post-treatment) to determine if any new AEs have occurred. After this period, Investigators should report only SAEs that are considered to be related to study treatment (AG-120/placebo or azacitidine).
- 10 Height at Screening only. Weight and body surface area calculation should be conducted on Day 1 of each cycle, prior to dosing.
- 11 Vital signs (temperature, BP [sitting for 5 minutes], pulse rate, respiratory rate) are to be taken at Screening and at any point when abnormal vital signs are suspected. All clinically relevant abnormal vital sign results will be reported as AEs.

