7.7.1. Primary Endpoint

7.7.1.1. Primary Analyses for EFS

EFS is defined as the time from randomization until TF, relapse from remission, or death from any cause, whichever occurs first. TF is defined as failure to achieve CR by Week 24. Subjects who do not achieve CR by Week 24 will be considered to have had an EFS event at Day 1 of randomization. For subjects who achieve CR by Week 24 (responders), the EFS time will be the time from randomization to relapse or death, whichever occurs first.

EFS will be tested using the log-rank test stratified by the randomization stratification factors. The basis for a claim of efficacy will be the statistical significance of EFS in favor of the AG-120+azacitidine arm when the 1-sided p-value <0.025.

Kaplan-Meier estimates (product-limit estimates) will be presented by treatment arm together with a summary of associated statistics. In particular, the EFS rate at 1 day, and 3, 6, 9, 12, 18, 24 and 36 months will be estimated with corresponding 2-sided 95% CIs. The CIs for the survival function estimates at the time points defined above will be derived using the log-log transformation (conftype=loglog default option in SAS PROC LIFETEST) with back transformation to a CI on the untransformed scale. The estimate of the standard error (SE) will be computed using Greenwood's formula.

The HR will be estimated using a Cox's proportional hazards (PH) model stratified by the randomization strata. Each stratum will define a separate baseline hazard function (using the "STRATA" statement in SAS PROC PHREG), ie for the i-th stratum the hazard function is expressed as: $h(i;t)=h(i,0;t)\exp(x\beta)$, where $h(i,0;t)$ defines the baseline hazard function for the i-th stratum and x defines the treatment arm (0= control arm, 1=treatment arm) and β is the unknown regression parameter. Ties will be handled by replacing the proportional hazards model by the discrete logistic model (Ties=Discrete option in SAS PROC PHREG). Given that the PH assumption is not met based on the EFS definition, the overall HR may not be meaningful.

As EFS is a composite endpoint, the estimates for each component will be summarized:

- CR rate by 24 weeks (following the methodology outlined in Section 7.7.2.1 without presenting p-values)
- EFS among subjects who achieve CR by 24 weeks (following the methodology outlined above restricted only to subjects who achieve CR by 24 weeks without

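### The 24-week CR limit in the primary endpoint runs from randomization but the visit weeks run from first dose, so a first CR at a compliant Week 25 visit can be scored as treatment failure

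*SAP*

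**What the plan says.** SAP 7.7.1.1.1 accepts CR by 24 weeks when the "date of first CR is within 25 weeks (24 weeks target+1 week window) after the date of randomization", which it writes as a difference of at most 24×7+7 days. The reason it gives is "The protocol allows a 1-week window for disease assessments". Footnote a to SAP Table 5 likewise ties the extra week to the protocol's schedule of assessments.

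Disease assessments are due on Day 1, with 7 days either way, "of Weeks 9, 17, 25, 33, 41, 53, and every 24 weeks thereafter". The protocol fixes where those weeks start. Table 6 labels Cycle 1 Day 1 as Week 1 and puts randomization in the screening column. Its footnote 8 says: "Subjects should start study treatment (ie, C1D1 [Week 1]) within 3 days (72 hours) of randomization". Protocol 9.7 adds: "The first day of study treatment dosing is considered Day 1 of a cycle". Later cycle delays do not move the visits: "The disease assessment schedule should not be altered due to changes in the start of treatment cycles" (Protocol 7.1).

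The consequence of missing the limit is in SAP 7.7.1.1: "Subjects who do not achieve CR by Week 24 will be considered to have had an EFS event at Day 1 of randomization".

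**The concern.** The extra week exists so that a Week 25 marrow taken within its window still counts. It does that only if Week 1 Day 1 is the day of randomization. When dosing starts 1 to 3 days later, the visit window moves with it and the limit does not.

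The penalty is all or nothing. A subject with a first CR one day past the limit changes from a responder, for whom the design assumes a median EFS of 14.6 or 19.2 months, to an event at Day 1. In the two component summaries the subject stays in the denominator of the 24-week CR rate as a non-responder and is removed from EFS among responders. None of the five EFS sensitivity analyses in SAP 7.7.1.2 varies the limit; the fifth changes only the event time given to treatment failures. The misclassification would therefore not show in the planned output.

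**Working it through.** **Inputs.** Limit of 24×7+7 days from randomization (SAP 7.7.1.1.1). Assessment window of ±7 days (Protocol 7.1, Table 6). Week 1 Day 1 = C1D1, lag L of 0 to 3 days after randomization (Protocol Table 6 footnote 8, Protocol 9.7). CR by 24 weeks of 20% and 40% in 200 subjects randomized 1:1 (SAP 6.2.1).

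**1. The SAP's figure.** If Week 1 Day 1 were the randomization date, Week 25 Day 1 would be 24×7 = 168 days later and the late edge of its window 168 + 7 = 175. This reproduces the SAP limit exactly.

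**2. The same visit on the protocol's clock.** Late edge = L + 168 + 7, in days from randomization:

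| Lag L (days) | Week 25 Day 1 | Last compliant day | Compliant days beyond 175 |
|---|---|---|---|
| 0 | 168 | 175 | 0 of 15 |
| 1 | 169 | 176 | 1 of 15 (6.7%) |
| 2 | 170 | 177 | 2 of 15 (13.3%) |
| 3 | 171 | 178 | 3 of 15 (20%) |

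Example: first dose 3 days after randomization, Week 25 marrow at +7 days, first CR. That is day 3 + 168 + 7 = 178. Since 178 > 175, the subject is scored as a treatment failure at Day 1.

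**3. How many subjects.** Expected responders: 100×0.20 + 100×0.40 = 60. The documents do not give the share of first CRs found at Week 25, the distribution of lags, or the spread of visit dates. Assuming visits spread evenly over the window:

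- 10% of first CRs at Week 25, everyone lagging 1 day: 60 × 0.10 × 1/15 = 0.4 subjects.
- One third at Week 25, lags 0 to 3 equally likely (mean rejected fraction (0+1+2+3)/4/15 = 0.10): 60 × 1/3 × 0.10 = 2 subjects.
- 50% at Week 25, everyone lagging 3 days: 60 × 0.50 × 3/15 = 6 subjects. This is a deliberate extreme.
- Everyone dosed on the day of randomization: 0 subjects.

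**4. Effect on power.** EFS was simulated under the SAP's assumptions, removing the same fraction of responders in each arm. Dropout was handled in two ways, because the documents do not say how it was simulated:

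| Responders lost | Dropout in responders only, unstratified test (5,000 runs) | 5% of all subjects censored, stratified test with assumed strata mix (6,000 runs) |
|---|---|---|
| 0 | 82.8% | 73.9% |
| 1% | 82.4% | 73.5% |
| 3.3% (2 of 60) | 81.2% | 72.3% |
| 6.7% (4 of 60) | 79.0% | 70.5% |

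The losses are about 0.5, 1.6 and 3.4 to 3.8 points. The two baselines bracket the planned 80%, so no error is claimed in that figure.

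**The case against.** The strongest reply is that the rule is explicit and follows the endpoint's own clock. EFS runs from randomization, 24×7+7 = 175 is correct arithmetic, and the missed-assessment rule in the same SAP section also counts its weeks from randomization. The SAP already allows 7 days beyond a literal 24 weeks. This stands as far as it goes: the SAP is consistent with itself, and nobody has miscalculated. It does not remove the mismatch. Sites schedule marrows from C1D1, and the SAP justifies its extra week by the protocol's window. Other text also uses the dosing clock: Protocol 8.5.1 describes treatment failure in terms of time on treatment, and SAP 6.3.3 counts study day from the start of treatment.

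A second reply is that few visits reach the rejected days. General study visits have a ±3-day window, so a marrow done at an undelayed Cycle 7 Day 1 visit falls by C1D1 + 171, at most day 174 from randomization. Only marrows done apart from that visit, or after cycle delays, are exposed. This stands. It makes the even-spread assumption used in the count pessimistic.

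A reader might infer that the rule is biased between arms, because twice as many responders are expected on AG-120. The documents do not support that. The limit is identical in both arms of a blinded trial. If a similar fraction of responders is lost in each, the ratio of CR rates is unchanged and the difference shrinks slightly. Nor is the key secondary CR rate at risk: SAP 7.7.2.1 sets no 24-week limit.

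**Conclusion.** The mismatch is real and narrow. It affects only subjects dosed at least one day after randomization whose first CR is documented on the last one to three days of a compliant Week 25 window. For them the primary endpoint changes from responder to an event at Day 1.

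The likely number is zero to a few. Any count rests on an assumed share of first CRs at Week 25 and an assumed spread of lags and visit dates, none of which the documents supply. At about 2 of 60 responders the simulated loss is about 1.6 points of power; at 1% of responders it is about half a point. The direction is a small dilution of the effect, with no mechanism for inflating type I error. The point merits correction because the primary test gates every key secondary test and the change is easy to make.

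**What to change.** Before unblinding, amend SAP 7.7.1.1.1 and footnote a to Table 5 so that CR by 24 weeks means date of first CR minus date of randomization ≤ 24×7+7+3 = 178 days. This keeps the randomization anchor and covers every compliant Week 25 visit. It does not reach the next scheduled assessment, whose earliest day is 32×7 − 7 = 217. The cost is that a subject dosed on the day of randomization may have a visit up to 3 days outside the window accepted.

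An alternative, not equivalent, is date of first CR minus C1D1 ≤ 175, using randomization for subjects never dosed. It matches the visit window exactly. However, it ties responder status to a post-randomization date, and it has no 3-day cap for late starters, because footnote 8 is worded as a recommendation.

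Under either choice:

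- Keep EFS time measured from randomization.
- Report the present 175-day rule as a sensitivity analysis.
- Align the minimum follow-up at data cutoff (SAP 2 and 6.2.2) with the CR window. It is 24 weeks, or 168 days, already 7 days short of the 175-day limit, and would be 10 days short of 178. On the planned timetable (accrual to month 44, analysis at month 52) the last subject would have about 8 × 30.4375 = 243 days, so this should cost no time.

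No new data are needed.
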